#### 6.1.4. Safety Assessments

Safety assessments will include monitoring of AEs, vital signs measurements, physical examinations, ECGs, and clinical laboratory studies as described in Section 11.3. Safety surveillance reporting of AEs commences at the time that informed consent is obtained and continues through the Post-Treatment Visit.

#### 6.1.5. Tumor Assessment

For tumor assessment, all sites of disease should be assessed radiologically according to RECIST, Version 1.1 using computed tomography (CT) or magnetic resonance imaging (MRI) at screening; after every even cycle, until the occurrence of disease progression. CT or MRI scans obtained as standard of care prior to informed consent will not need to be repeated if performed within 14 days prior to dosing. Assessments should be performed within 7 days

of starting the subsequent cycle. Additional scans may be obtained at the discretion of the investigator, if clinically indicated. If a patient shows a radiological response (complete response [CR] or partial response [PR]), a confirmatory radiological assessment will be performed at least 4 weeks after the response was first noted. For patients who have a confirmed CR, it is strongly recommended that they receive prophylactic cranial irradiation (PCI) after completion of chemotherapy. Patients with a confirmed PR should also consider PCI after completion of chemotherapy based on the investigator's judgment (see Section 8.8). For those patients who have not progressed at the time of study drug discontinuation, tumor assessments, including all sites of disease, will be assessed radiologically by CT or MRI, as performed at screening, every 2 months (approximately  $60 \pm 7$  days) until the occurrence of progressive disease or study completion. The same method of assessment (CT or MRI) should be used to characterize tumors at screening and at all follow-up assessments. If positron emission tomography (PET) is used, it should also be accompanied by spiral CT or MRI. Tumor assessment is further described in Section 11.5.

## 7. STUDY POPULATION

### 7.1. Selection of Patients

Overall, up to 110 patients will be enrolled in the study.

In Part 1, approximately 40 patients will be enrolled, assuming up to 3 cohorts. Cohorts will consist of 6 patients each in the Phase 1b dose-finding portion of Part 1 and up to 18 patients in the Phase 2a expansion portion of Part 1 at the selected dose to be used in Part 2.

Additional patients may be enrolled in the Phase 1b dose-finding portion of Part 1 if more than 1 cohort is enrolled.

In Part 2, 70 patients will be randomly assigned (1:1 ratio) to 1 of 2 groups: G1T28 administered IV with E/P therapy (Group 1) or placebo administered IV with E/P therapy (Group 2).

The study will be conducted at up to 80 centers in North America and Europe.

#### 7.1.1. Inclusion Criteria

For a patient to be eligible for participation in this study, *all* of the following criteria must apply.

1. Age  $\geq$  18 years
2. Unequivocally confirmed diagnosis of SCLC by histology or cytology, preferably including the presence of neuroendocrine features by immunohistochemistry
3. Extensive-stage disease
4. At least 1 target lesion that is unirradiated and measurable by RECIST, Version 1.1 ([Eisenhauer 2009](#))
5. Hemoglobin  $\geq$  9.0 g/dL
6. Absolute neutrophil count  $\geq$   $1.5 \times 10^9$ /L
7. Platelet count  $\geq$   $100 \times 10^9$ /L
8. Creatinine  $\leq$  1.5 mg/dL OR glomerular filtration rate (GFR) of  $\geq$  60 mL/min (by Cockcroft-Gault formula [[Cockcroft and Gault 1976](#)]); creatinine clearance calculated from an isotopic method or a 24-hour urine collection may be used instead of an estimated GFR by the Cockcroft-Gault formula
9. Total bilirubin  $\leq$   $1.5 \times$  upper limit of normal (ULN)
10. AST and ALT  $\leq$   $2.5 \times$  ULN;  $\leq$   $5 \times$  ULN in the presence of liver metastases
11. Serum albumin  $\geq$  3 g/dL

12. Eastern Cooperative Oncology Group (ECOG) performance status of 0 to 2
13. Predicted life expectancy of  $\geq 3$  months
14. Contraception:
  - a. For females: All females of childbearing potential must have a negative serum beta human chorionic gonadotropin ( $\beta$ -hCG) test result at screening and at baseline. Females must be either postmenopausal, surgically sterile, or using an acceptable method of contraception. Acceptable surgical sterilization techniques are hysterectomy, bilateral tubal ligation with surgery at least 6 months prior to dosing, and bilateral oophorectomy, with surgery at least 2 months prior to dosing. Acceptable methods of contraception are an intrauterine device, contraceptive implant, oral contraceptive (stable dose of the same hormonal contraceptive product for at least 3 months prior to dosing), a vasectomized partner, and a barrier method (condom or diaphragm) during the study and for 3 months after discontinuation of treatment
  - b. For males: Patients with female partner of childbearing potential must agree to use a highly effective form of birth control, which entails the use of oral, injected, or implanted hormonal methods of contraception or an intrauterine device/system by the female partner, in combination with a barrier method (eg, condom, diaphragm, cervical cap) during the study and for 3 months after discontinuation of treatment, and will also refrain from sperm donation for 3 months following completion of the study
15. Able to understand and sign an informed consent

#### 7.1.2. Exclusion Criteria

A patient will not be eligible for participation in this study if *any* of the following criteria apply.

1. Prior chemotherapy for limited or extensive-stage SCLC
2. Presence of symptomatic brain metastases requiring immediate treatment with radiation therapy or steroids
3. History of other malignancies, except for the following: (1) adequately treated basal or squamous cell carcinoma of the skin; (2) curatively treated a) in situ carcinoma of the uterine cervix, b) prostate cancer, or c) superficial bladder cancer; or (3) other curatively treated solid tumor with no evidence of disease for  $\geq 3$  years
4. Uncontrolled ischemic heart disease or uncontrolled symptomatic congestive heart failure (Class III or IV as defined by the New York Heart Association [NYHA] functional classification system)
5. Known history of stroke or cerebrovascular accident within 6 months prior to enrollment
6. Serious active infection

7. Psychiatric illness/social situations that would limit study compliance
8. Other uncontrolled serious chronic disease or conditions that in the investigator's opinion could affect compliance or follow-up in the protocol
9. Known human immunodeficiency virus (HIV), known hepatitis B virus (HBV), or known hepatitis C virus (HCV) positive that is symptomatic or requiring active therapy
10. Concurrent radiotherapy to any site or radiotherapy within 2 weeks prior to enrollment or previous radiotherapy to the target lesion sites (the sites that are to be followed for determination of a response)
11. Receipt of any investigational medication within 4 weeks prior to enrollment
12. Hypersensitivity to any of the components of the formulation of etoposide or etoposide phosphate
13. Hypersensitivity to cisplatin or other platinum-containing compounds, or mannitol
14. Legal incapacity or limited legal capacity
15. Pregnant or lactating women

Patients may withdraw from study drug or from the study at their own discretion (or at the discretion of the investigator) for any reason at any time (see Section [12.3](#) and [12.4](#)).

## 8. TREATMENTS

### 8.1. Treatments Administered

The initial group of patients in Part 1 of the study will receive G1T28 200 mg/m^2 administered IV once daily on Days 1 to 3 of each 21-day E/P chemotherapy cycle. All dose escalation/de-escalation decisions and additional cohorts of patients to be enrolled in the Phase 1b dose-finding portion of Part 1, if any, will be based on Cycle 1 safety and available PK data (see Section 6.1.1). If the G1T28 dose level for a subsequent cohort is adjusted by the SMC, the SMC may also recommend that all patients currently receiving G1T28 in combination with E/P therapy should have their G1T28 dose adjusted accordingly, starting with their next scheduled cycle.

Patients enrolled to the Phase 2a expansion portion of Part 1 and Part 2 will receive the dose of G1T28 derived from the Phase 1b dose-finding portion of Part 1 or placebo administered IV once daily on Days 1 to 3 of each 21-day E/P chemotherapy cycle. There will be no inpatient dose modifications of G1T28 in the Phase 2a expansion portion of Part 1 and Part 2 of the study.

Patients will receive standard E/P chemotherapy in 21-day cycles. The carboplatin dose will be calculated using the Calvert formula with a target AUC = 5 (maximum 750 mg) IV on Day 1, and 100 mg/m^2 etoposide will be administered IV daily on Days 1, 2, and 3 of each 21-day cycle.

**The interval between doses of G1T28 or placebo on successive days should not be greater than 28 hours. The interval between the dose of G1T28 or placebo and the first dose of chemotherapy on a given day (etoposide or carboplatin) should not be greater than 4 hours.**

**G1T28 or placebo will only be administered with E/P therapy. If administration of E/P therapy is discontinued, G1T28 or placebo will also be discontinued.**

**Chemotherapy cannot be administered until after completion of the G1T28 or placebo infusion. If the second or third dose of G1T28 or placebo in any given cycle is not administered for any reason, do not administer the dose of etoposide chemotherapy on that day, since this could potentially exacerbate myelosuppression (see Section 8.4.4.1).**

Study drug administration will continue until disease progression, unacceptable toxicity, withdrawal of consent, or discontinuation by investigator (eg, after completing 6 cycles), whichever occurs first. Treatment cycles will occur consecutively without interruption, except when necessary to manage toxicities or for up to a 1 week delay for administrative reasons, for a maximum total delay of up to 2 weeks. If the subsequent cycle is delayed, the patient should still complete the clinical laboratory assessments and the FACT-L and FACT-An questionnaires on the scheduled Day 1, as well as on the actual first dosing day of the next cycle.

Patients should meet the laboratory parameter requirements outlined in Section 10.4 before initiation of Cycle 2 and each subsequent cycle of E/P therapy. All nonhematologic

drug-related toxicities (except alopecia) should have resolved to Grade 1 or baseline before initiation of the next cycle of E/P therapy.

## **8.2. Investigational Products**

### **8.2.1. Identity**

#### **8.2.1.1. G1T28**

G1T28 is supplied as a single-use, sterile powder with 40 or 100 mg G1T28 in each 10-mL flint glass vial. D-mannitol, USP is added as a cake forming agent and citrate buffer is added to maintain the reconstituted pH at 4.0 to 5.0. The process for reconstitution of study drug is detailed in the Pharmacy Manual.

#### **8.2.1.2. Placebo**

The placebo formulation of 250 mL of dextrose 5% in water (D5W) or sodium chloride solution 0.9% will be prepared by the pharmacist/designee on site.

#### **8.2.1.3. Etoposide and Carboplatin**

Descriptions of the formulations of commercially-available etoposide and carboplatin can be found in the respective current prescribing information (see [Appendix 2](#)).

### **8.2.2. Packaging and Labeling**

#### **8.2.2.1. G1T28**

G1T28 sterile powder is manufactured and packaged by University of Iowa Pharmaceuticals, Iowa City, Iowa, United States of America.

Individual vials of G1T28 will be labeled and supplied to the unblinded pharmacist/designee who will inventory the contents and document them according to the drug accountability requirements (Section [8.2.5](#)).

#### **8.2.2.2. Placebo**

The placebo formulation of 250 mL of D5W or sodium chloride solution 0.9% will be prepared by the pharmacist/designee on site, and labeled with the randomization number.

#### **8.2.2.3. Etoposide and Carboplatin**

Descriptions of the packaging and labeling of commercially-available carboplatin and etoposide can be found in the respective current prescribing information (see [Appendix 2](#)).

### 8.2.3. **Storage**

#### 8.2.3.1. G1T28

The G1T28 sterile powder 40-mg/10 mL or 100-mg/10 mL vial should be stored refrigerated at 2°C to 8°C.

Stability data for the current formulation of G1T28 sterile powder 40-mg/10 mL vial demonstrates satisfactory stability for up to 6 months at 5°C and 25°C/60% relative humidity (RH). Based on these data, stability is expected to exceed 18 months at refrigerated storage conditions.

Stability data for the current formulation of G1T28 sterile powder 100-mg/10 mL vial demonstrates satisfactory stability for up to 1 month at 40°C/75% RH. Based on these data, stability is expected to exceed 12 months at refrigerated storage conditions.

Study drugs will be stored in a locked refrigerator under applicable storage conditions at the site and only the pharmacist/designee and designated personnel will have access to the study drugs.

#### 8.2.3.2. Placebo

The placebo formulation of 250 mL of D5W or sodium chloride solution 0.9% will be stored identically to G1T28 to protect the integrity of the blind.

#### 8.2.3.3. Etoposide and Carboplatin

Information regarding the storage of commercially-available carboplatin and etoposide can be found in the respective current prescribing information (see [Appendix 2](#)).

### 8.2.4. **Procedure for Dispensing**

Dispensing instructions, including instructions for masking the G1T28 or placebo infusion bags, will be provided in the Pharmacy Manual and will be maintained in the pharmacy records.

### 8.2.5. **Investigational Product Accountability**

The pharmacist/designee will verify the integrity of the clinical trial supplies (storage conditions, correct amount received, condition of shipment, kit numbers, etc.) according to the investigative site's standard operating procedures (SOPs).

At a minimum, the following data will be tracked on the drug accountability log at the site pharmacy:

- Date received
- Lot number
- Vial number
- Date dispensed

- Patient number
- Identification of the person dispensing the drug

Records of study medication (used, lost, destroyed, and returned containers, individual vials) should be made at each visit in the drug accountability and dispensing forms. Drug accountability and reconciliation will be checked and verified by the pharmacy team during the study and by the site monitor during and at the completion of the study.

Once the site monitor has verified drug accountability at the site, any used drug remaining at the completion of the study will be destroyed. Unused and unopened study medication will be returned by the site monitor to the sponsor or may be destroyed on site according to the investigative site's SOPs.

### **8.3. Method of Assigning Patients to Treatment Groups**

A unique patient identification number (screen number) will be assigned to each patient who signs an informed consent form. Once a patient is determined eligible, ie, meets all inclusion/exclusion criteria, an enrollment number will be assigned by an interactive web-response system (IWRS).

Part 1 of the study (dose-finding and expansion cohorts) is open-label and there will be no randomization.

Part 2 is randomized and blinded. Patients meeting all inclusion and exclusion criteria in Part 2 will be randomized 1:1 to receive G1T28 or placebo as described in Section 8.5. Each patient will be assigned a unique randomization number, which will not be reused.

### **8.4. Dose, Dosing Regimen, and Route**

#### **8.4.1. G1T28**

The starting dose level for the Phase 1b dose-finding portion of Part 1 will be 200 mg/m^2, which is derived from the G1T28-1-01 study, a Phase 1a safety, PK, and pharmacodynamic study of G1T28 in healthy male and female subjects. See Section 6.1 for possible dose escalation/de-escalation decisions based on safety and available PK data.

G1T28 diluted in 250 mL of D5W or sodium chloride solution 0.9% is to be administered by IV infusion over 30 minutes. If there is any study drug remaining in the infusion bag at the end of the 30 minutes, the infusion should be continued at the same rate until the entire contents of the bag have been administered to ensure patients receive the full dose. Details regarding the reconstitution and dilution of G1T28 vials are detailed in the Pharmacy Manual.

**The interval between doses of G1T28 on successive days should not be greater than 28 hours. G1T28 will only be administered with E/P therapy. If administration of E/P therapy is discontinued, G1T28 will also be discontinued.**

#### 8.4.2. **Placebo**

The placebo formulation of 250 mL of D5W or sodium chloride solution 0.9% will be administered over 30 minutes. If there is any volume remaining in the infusion bag at the end of the 30 minutes, the infusion should be continued at the same rate until the entire contents of the bag have been administered to ensure patients receive the full dose.

**The interval between doses of placebo on successive days should not be greater than 28 hours. Placebo will only be administered with E/P therapy. If administration of E/P therapy is discontinued, placebo will also be discontinued.**

#### 8.4.3. **Etoposide and Carboplatin**

Etoposide and carboplatin will be administered IV in accordance with the prescribing information (see [Appendix 2](#)) and according to the study site's standard practice.

Needles or IV administration sets containing aluminum parts that may come in contact with carboplatin should not be used for the preparation or administration of the drug. Aluminum can react with carboplatin causing precipitate formation and loss of potency.

**The interval between the dose of G1T28 or placebo and the first dose of chemotherapy on a given day (etoposide or carboplatin) should not be greater than 4 hours.**

**Chemotherapy cannot be administered until after completion of the G1T28 or placebo infusion. If the second or third dose of G1T28 in any given cycle is not administered for any reason, do not administer the dose of etoposide chemotherapy on that day, since this could potentially exacerbate myelosuppression (see Section [8.4.4.1](#)).**

##### 8.4.3.1. Carboplatin

The carboplatin dose will be calculated using the Calvert formula with a target AUC = 5 on Day 1 of each 21-day cycle and administered as an IV infusion over 30 minutes. The Calvert formula is as follows:

$$\text{Total carboplatin dose (mg)} = (\text{target AUC}) \times (\text{GFR} + 25)$$

Because each patient's estimated GFR will be based on serum creatinine measurements obtained using standardized isotope dilution mass spectrometry, the **dose of carboplatin should be capped at 750 mg** to avoid potential toxicity due to overdosing. The cap dose of 750 mg for carboplatin is based on a GFR estimate that is capped at 150 mL/min for patients with normal renal function (ie, maximum carboplatin dose = target AUC of 5 mg•min/mL × 150 mL/min = 750 mg).

Refer to the carboplatin prescribing information (see [Appendix 2](#)) for details regarding preparation, administration, instructions and precautions. Premedications may be provided per local standard of care.

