	
immediate treatment with radiation therapy or steroids
 
 
3. History of other malignancies, except for the following: (1) adequately treated basal or squamous cell carcinoma of the skin; (2) curatively treated a) in situ carcinoma of the uterine cervix, b) prostate cancer, or c) superficial bladder cancer; or (3) other curatively treated solid tumor with no evidence of disease for <math>\geq 3</math> years
 
4. Uncontrolled ischemic heart disease or uncontrolled symptomatic congestive heart failure (Class III or IV as defined by the New York Heart Association [NYHA] functional classification system)
 
5. Known history of stroke or cerebrovascular accident within 6 months prior to enrollment
 
6. Serious active infection
 
7. Psychiatric illness/social situations that would limit study compliance
 
8. Other uncontrolled serious chronic disease or conditions that in the investigator's opinion could affect compliance or follow-up in the protocol
 
9. Known human immunodeficiency virus (HIV), known hepatitis B virus (HBV), or known hepatitis C virus (HCV) positive that is symptomatic or requiring active therapy
 
10. Concurrent radiotherapy to any site or radiotherapy within 2 weeks prior to enrollment or previous radiotherapy to the target lesion sites (the sites that are to be followed for determination of a response)
 
11. Receipt of any investigational medication within 4 weeks prior to enrollment
 
12. Hypersensitivity to any of the components of the formulation of etoposide or etoposide phosphate
 
13. Hypersensitivity to cisplatin or other platinum-containing compounds, or mannitol
 
14. Legal incapacity or limited legal capacity
 
15. Pregnant or lactating women
 

Chemotherapy Treatment	Carboplatin dose calculated using the Calvert formula with a target AUC = 5 (maximum dose of 750 mg) administered IV over 30 minutes on Day 1 and 100 mg/m  etoposide administered IV over 60 minutes daily on Days 1, 2, and 3 of each 21-day cycle
Test Articles Dosage and Administration	A starting dose of G1T28 200 mg/m  in 250 mL of dextrose 5% in water (D5W) or in sodium chloride solution 0.9% administered as an IV infusion over 30 minutes once daily on Days 1 to 3 of each 21-day cycle prior to the dose(s) of chemotherapy

---

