#### 6.1.1.2. Criteria for Adjusting G1T28 Dose Based on Pharmacokinetic Parameters

The PK profile of G1T28 is well established in healthy subjects, with good estimates of key parameters such as  $C_{max}$ , AUC, and CL. In addition, the intersubject variability in these PK parameters is low (see Section 4.2). However, patients with SCLC enrolled in this study will likely be older and have more comorbidities compared with subjects enrolled in the Phase 1a G1T28-1-01 study, and therefore, could demonstrate differences in PK.

Based on the observed PK profile of G1T28 in Study G1T28-1-01, the extrapolated  $AUC_{0-24.5h}$  for a 200 mg/m^2 dose is 3100 h•ng/mL. If the mean  $AUC_{0-24.5h}$  in the initial cohort of patients (6 patients) in the Phase 1b, dose-finding portion of Part 1 is not within 20% of the target (eg, 2480 to 3720 h•ng/mL), then the dose of G1T28 will be adjusted in the next cohort of 6 patients to achieve a mean  $AUC_{0-24.5h}$  of 3100 h•ng/mL. The magnitude of the dose modification is based upon the fact that G1T28 displays linear PK over the dose range studied to date. Any available PK data from additional cohort(s) of the Phase 1b dose-finding portion of Part 1 may be utilized for modifying the G1T28 dose (if required). If the G1T28 dose level for a subsequent cohort requires escalation, the increase will not exceed 30% from the previous dose level. A G1 cell cycle arrest of a minimum of 24 hours after G1T28 administration is desired to ensure that the bone marrow arrest is maintained long enough to avoid releasing HSPCs into the S (DNA synthesis) phase of the cell cycle in the presence of high concentrations of chemotherapy and thereby potentially exacerbating myelosuppression.

If the dose is adjusted due to DLTs and the PK was within the expected target range, then a new target  $AUC_{0-24.5h}$  will be calculated for the modified dose as follows:

$$Y = 2.11 + 1.1 * X, \text{ where } Y \text{ is the } \ln(AUC_{0-24.5}) \text{ h} \cdot \text{ng/mL} \text{ and } X \text{ is the } \ln(\text{dose}) \text{ mg/m}^2$$

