**Table 8-1 Etoposide and Carboplatin Dose Reductions**

Dose level	Etoposide (mg/m  )	Carboplatin (AUC)
Dose level -1 (first dose reduction)	Reduce to 75 mg/m 	Reduce to AUC = 4
Dose level -2 (second dose reduction)	Reduce to 50 mg/m 	Reduce to AUC = 3

AUC = area under the concentration-time curve

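### Protocol 8.4.3.1 misstates the GFR behind the 750 mg carboplatin cap: the printed formula puts it at 125 mL/min, not 150

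*Protocol*

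**What the plan says.** Protocol 8.4.3.1 prints the Calvert formula: dose in mg equals target AUC times (GFR + 25), with a target AUC of 5. It then instructs that the "dose of carboplatin should be capped at 750 mg". The reason given is that GFR will be estimated from serum creatinine and the cap is there "to avoid potential toxicity due to overdosing".

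The next sentence explains where 750 mg comes from. The cap is "based on a GFR estimate that is capped at 150 mL/min for patients with normal renal function", and the sum is shown as "maximum carboplatin dose = target AUC of 5 mg•min/mL × 150 mL/min = 750 mg".

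The 750 mg maximum also appears in the Synopsis (Chemotherapy Treatment) and in Section 8.1 ("Calvert formula with a target AUC = 5 (maximum 750 mg) IV on Day 1"). Both places tie it to AUC 5 and neither mentions a GFR cap. Table 8-1 lowers the carboplatin target in two steps, first "Reduce to AUC = 4" and then to AUC 3. It gives no maximum in mg at either step.

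**The concern.** The formula and the explanation of the cap stand a few lines apart and do not agree. The explanation names the quantity (a GFR estimate), gives its unit and says it is capped at 150. The formula adds 25 to GFR before multiplying, but the worked sum multiplies AUC by 150 directly. So either the sum leaves out the 25, or the 150 is not a GFR.

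At AUC 5 the explicit 750 mg limit settles the dose. At reduced AUC the 150 mL/min figure is the only GFR limit in the dosing section, and a site could put it into the formula. The patients concerned have a high estimated GFR and are being reduced for toxicity. The cap was written because a creatinine-based estimate may be too high.

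**Working it through.** **Inputs**, all from the Protocol: dose = AUC × (GFR + 25), target AUC 5, cap 750 mg and stated GFR cap 150 mL/min (8.4.3.1); reduced targets AUC 4 and AUC 3 (Table 8-1).

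**1. The plan's own figure.** 5 × 150 = 750 mg. This is reproduced only by leaving out the + 25.

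**2. The stated GFR cap in the printed formula.** 5 × (150 + 25) = 5 × 175 = 875 mg, and 875 / 750 = 1.167. The result is 16.7% above the stated cap.

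**3. The GFR that 750 mg implies.** 750 = 5 × (GFR + 25), so GFR = 750 / 5 − 25 = 125 mL/min. The 150 in the worked sum is therefore 125 + 25.

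**4. Full dose.** At an estimated GFR of 140 the formula gives 5 × 165 = 825 mg. The stated GFR limit has not been reached, yet the dose is held to 750 mg. The 750 mg cap binds from GFR 125 upward, so the dose given at AUC 5 is the same whichever GFR figure is printed.

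**5. Reduced dose.** Maximum dose in mg under each reading:

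| Reading | AUC 5 | AUC 4 | AUC 3 |
|---|---|---|---|
| GFR capped at 125 | 750 | 4 × 150 = 600 | 3 × 150 = 450 |
| Worked sum scaled, AUC × 150 | 750 | 600 | 450 |
| GFR capped at 150 in the formula | 875, held to 750 | 4 × 175 = 700 | 3 × 175 = 525 |
| Flat 750 mg only | 750, binds at GFR 125 | 750, binds at GFR 162.5 | 750, binds at GFR 225 |

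The binding points in the last row are 750 / AUC − 25. At an estimated GFR of 125 or below, all readings give the same dose. The 150 reading exceeds the 125 reading by 700 / 600 = 525 / 450 = 1.167.

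**6. Delivered AUC when the estimated GFR is 150.** Delivered AUC = dose / (true GFR + 25). The true GFR values are assumptions; the documents give none.

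| True GFR | 700 mg | 600 mg | 525 mg | 450 mg |
|---|---|---|---|---|
| 150 | 4.00 | 3.43 | 3.00 | 2.57 |
| 125 | 4.67 | 4.00 | 3.50 | 3.00 |
| 100 | 5.60 | 4.80 | 4.20 | 3.60 |

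If the estimate is accurate, 700 and 525 mg meet the Table 8-1 targets exactly, and 600 and 450 mg fall short of them. If the estimate is too high, the order reverses: 700 and 525 mg overshoot, by more than 600 and 450 mg do.

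**The case against.** The best case on the other side is that the wrong number is explanation, not instruction. The operative rule is 750 mg. It appears in three places and is correct. A site would have to turn an explanatory sentence into a rule for other AUC levels, then put 150 into a formula that the same sentence does not use. Scaling the sentence's own sum gives 600 and 450 mg, the same as a GFR cap of 125. Sections 8.4.3 and 8.4.3.1 also send sites to the prescribing information, and 8.4.3 to site standard practice. Neither can be seen here, so sites may have other guidance.

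Most of this stands, and it is why the point is minor. It does not make the sentence right. The sentence gives a GFR limit with a unit, that limit contradicts the formula above it, and no other GFR limit is offered for dosing.

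Three stronger inferences are tempting, and the documents do not support them:

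- *Patients would receive 875 mg.* They would not; the explicit cap holds every AUC 5 dose at 750 mg.
- *The misstatement is why the maximum at reduced AUC is unclear.* It adds one reading (700 and 525 mg). With 125 printed, Table 8-1 would still have no mg maximum, and a flat or a scaled cap would still be open.
- *Patients reduced for toxicity would be overdosed.* That needs an estimate above the true GFR, and nothing in the documents says how often or by how much.

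**Conclusion.** The stated GFR basis is wrong as written. With the protocol's own formula, 750 mg at AUC 5 corresponds to 125 mL/min, and 150 mL/min would give 875 mg. This is arithmetic and needs no assumption.

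The practical reach is narrow. It takes an estimated GFR above 125 mL/min, a reduction to AUC 4 or AUC 3, and a site that applies the stated cap of 150. The maximum is then 700 or 525 mg in place of 600 or 450 mg. Inclusion criterion 8 sets no upper limit on GFR, so such patients can enroll. They may be few, because Section 6.1.1.2 expects that "patients with SCLC enrolled in this study will likely be older and have more comorbidities" than the healthy subjects of the Phase 1a study. No count is given.

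The planned analysis is not affected: SAP Table 9 computes carboplatin dose intensity from prescribed AUC, not mg. Severity is minor.

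**What to change.** **Correction.** In 8.4.3.1, replace 150 mL/min with 125 mL/min as the GFR cap, and write the sum as 5 × (125 + 25) = 750 mg. This costs one line. The 750 mg cap, Section 8.1, the Synopsis and the SAP stay as they are.

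**Optional query, separate from the error.** The sponsor could confirm whether the cap scales with target AUC (600 mg at AUC 4, 450 mg at AUC 3) or stays flat at 750 mg, and add the answer to Table 8-1. Each choice has a cost. Scaled maxima guard against an inflated estimate but deliver AUC 3.43 and 2.57 to a patient whose true GFR is 150. Under a flat cap, a patient with an estimated GFR of 162.5 or more still receives 750 mg at AUC 4, so the first carboplatin reduction changes nothing in mg. This is the sponsor's decision, and the correction above does not depend on it.
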